# **8.5.1.1.** Criteria for handling concentrations below the limit of quantification in Pharmacokinetic analysis

• Concentration values that are below the level of quantification (BLQ) will be set to 0, with defined exceptions as follows;

 Any embedded BLQ value (between 2 quantifiable concentrations) and BLQ values following the last quantifiable concentration in a profile will be set to missing for the purposes of PK analysis.

- o If there are late positive concentration values following 2 BLQ concentration values in the apparent terminal phase, these values will be evaluated. If these values are considered to be anomalous, they will be set to missing.
- o If an entire concentration-time profile is BLQ, the profile will be excluded from the PK analysis.
- o If a predose concentration is missing in Part A or on Day 1 of Part B, these values may be set to 0 with sponsor approval.

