## Secondary PK

- o minimum observed plasma concentration (Cmin)
- $\circ$   $t_{max}$
- $0 t_{1/2}$
- o observed accumulation ratio based on AUC0- $\tau$  (RAAUC0- $\tau$ )
- o observed accumulation ratio based on Cmax (RACmax).
- o Temporal change parameter (TCP)

Other PK parameters may also be added if deemed necessary.

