## 8.1.1. Calculation of the Summary Statistics

For continuous data the following rules will be applied:

- Missing values will not be imputed, unless specifically stated otherwise.
- Unrounded data will be used in the calculation of summary statistics.

• If number of subjects with valid observations (n) <3, summary statistics will not be calculated, with the exception of n, minimum, and maximum.

• As Early Termination data is not associated with any scheduled timepoint, it will be excluded from all calculations of summary statistics.

For categorical data the following rules will be applied:

- If the categories of a parameter are ordered (eg, AE severity), all categories between the possible minimum and maximum categories will be included, even if n = 0 for a given category. If the categories are not ordered (eg, race), only those categories for which there is at least 1 subject represented will be included.
- Missing values will not be imputed, with the exception of AEs where the 'worst-case' approach will be taken (see Section 8.7.1), or unless specifically stated otherwise. A 'missing' category will be included for any parameter for which information is missing. This will ensure that the population size totals are consistent across different parameters.

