## Part B

Parameter	Definition		
AUC 0-τ	area under the plasma concentration-time curve calculated over the dosing interval		
	$(\tau)$		
$\mathrm{AUC}_{0\text{-}\infty}$	area under the plasma concentration-time curve from time 0 extrapolated to infinity		
$%AUC_{extrap}$	percentage of AUC that is due to extrapolation from the last measurable plasma		
	concentration to infinity		
$C_{max}$	maximum observed plasma concentration		
$C_{trough}$	concentration observed at the end of the dosing interval		
$t_{max}$	time of maximum observed plasma concentration		
$t_{1/2}$	apparent plasma terminal elimination half-life		
$RAAUC_{0-\tau}$	observed accumulation ratio based on AUC 0-τ , calculated as AUC 0-τ on profile day		
	15 / AUC 0-τ on profile day 1		
$RAC_{max}$	observed accumulation ratio based on C max , calculated as C max on profile day 15 /		
	C max on profile day 1		
TCP	temporal change parameter, calculated as $AUC_{0-\tau}$ on profile day 15 / $AUC_{0-\infty}$ on		
	profile day 1		

The DN AUC0-∞, DN AUC0-tlast and DN Cmax will be calculated by dividing the original PK parameter by dose.

Additional PK parameters may be determined where appropriate.

The PK analysis will, where possible, be carried out using actual postdose times recorded in the raw data. If actual times are missing, nominal times may be used.

Concentrations are used as supplied by the analytical laboratory for PK analysis. The units of concentration and resulting PK parameters, with amount or concentration in the unit, will be presented as they are received from the analytical laboratory.

Cmax and tmax will be obtained directly from the plasma concentration-time profiles.

For multiple peaks, the highest postdose concentration will be reported as  $C_{max}$ . In the case that multiple peaks are of equal magnitude, the earliest  $t_{max}$  will be reported.

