## **8.5.1.2.2.** Goodness of Fit

- When assessing terminal elimination phases, the adjusted coefficient for determination of exponential fit (R^2-adj) will be used as a measure of the goodness of fit of the data points to the determined line.
- Regression based parameters (AUC0- $\infty$ , t1/2) will only be calculated if the R^2-adj  $\geq$ 0.7.

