#### 8.5.2. Presentation Pharmacokinetic Plasma Concentration Data

- The following rules will be applied if there are values that are BLQ or if there are missing values in a plasma concentration data series to be summarized.
  - o For the calculation of summary statistics, BLQ values will be set to 0.
  - o If an embedded BLQ value is considered anomalous within the concentration-time profile, this value will be excluded from the summary statistics.
  - If the value of the arithmetic mean or median is BLQ, these values will be presented as 0 and the geometric mean and geometric coefficient of variation will not be calculated.
  - o Concentrations collected with a time deviation from nominal time >10% will be reported and flagged but excluded from summary statistics.

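### The PK rule that sets BLQ values after the last quantifiable concentration to missing has no exception for Ctrough, so the Part B trough summary can describe only subjects with quantifiable troughs

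*SAP*

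**What the plan says.** Section 8.5.1.1 of the SAP governs BLQ handling when PK parameters are derived. By default BLQ values "will be set to 0, with defined exceptions as follows". One exception covers embedded BLQ values and also BLQ values "following the last quantifiable concentration in a profile will be set to missing for the" PK analysis. Another reads: "If an entire concentration-time profile is BLQ, the profile will be excluded from the PK analysis". None of the exceptions is limited to particular parameters.

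The Part B parameter table in Section 8.5.1 includes Ctrough, defined as the "concentration observed at the end of the dosing interval". Section 3.2 lists Cmin, the "minimum observed plasma concentration", as a secondary PK endpoint for Part B, but Cmin has no entry in the Section 8.5.1 table.

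Three other sections decide what then happens to a trough:

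- Section 8.1.1, for continuous data: "Missing values will not be imputed, unless specifically stated otherwise". With fewer than 3 valid observations, only n, minimum and maximum are given.
- Section 8.5.3 provides summary tables for every PK parameter that is not regression-related, which includes Ctrough.
- Section 8.5.2, for concentration tables: "For the calculation of summary statistics, BLQ values will be set to 0".

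**The concern.** Removing trailing BLQ values is a sensible convention for AUC to the last quantifiable time and for the terminal regression, where a run of zeros would distort the fit. Ctrough is different, because it is itself a single observed concentration at a fixed time. A trough below the LLOQ is a known low value, and treating it as absent discards information in one direction only.

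The subjects removed are always those with the lowest troughs, so the remaining mean and median overstate trough exposure, most of all at dose levels where troughs are low. The report could also carry two tables that disagree about the same samples: the concentration table at the trough time, with BLQ as 0, and the Ctrough table, with BLQ removed. No inferential PK analysis is planned, so these descriptive tables are the Part B PK result.

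**Working it through.** The SAP states no figure on this point, so there is none to reproduce. The check traces the rule through the text and then sizes it under stated assumptions.

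**Tracing the rule**

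1. Dosing on Days 1, 4, 7, 10 and 13 (Section 4.2) gives a planned interval of 3 × 24 = 72 h. Section 4.2 allows the frequency to change.
2. Take a profile that is quantifiable to 48 h and BLQ at 72 h. The times are illustrative, since the SAP gives no sampling schedule. The 72 h value comes after the last quantifiable one, so Section 8.5.1.1 sets it to missing.
3. Ctrough is the 72 h value, so Ctrough is missing. Section 8.1.1 does not impute it.
4. Section 8.5.3 summarises Ctrough from the remaining subjects. Section 8.5.2 enters the same sample as 0 in the concentration summary, unless another exclusion there applies.

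**Inputs for the size**

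- From the SAP: 6 active subjects per Part B group (Section 4.2); at least 3 values needed for a mean (Section 8.1.1).
- Assumed: lognormal troughs; between-subject CV of 30%, 50% or 80%; BLQ probability p of 1/3 or 1/2.

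**Formulas**

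With s = √ln(1 + CV²) and z_p the standard normal quantile at p:

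- Mean with BLQ missing ÷ true mean = Φ(s − z_p) / (1 − p)
- Median with BLQ missing ÷ true median = exp(s × z at (1 + p)/2)
- Mean with BLQ as 0 ÷ true mean = Φ(s − z_p)

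The values of s are 0.294, 0.472 and 0.703. For p = 1/3, z_p = −0.431 and the quantile at 2/3 is 0.431. For p = 1/2, z_p = 0 and the quantile at 3/4 is 0.674.

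Example, p = 1/3 and CV 30%: Φ(0.294 + 0.431) = 0.766. Mean ratio = 0.766 / 0.667 = 1.15. Median ratio = exp(0.294 × 0.431) = 1.13. With BLQ as 0, the mean ratio is 0.77.

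| BLQ share | CV | Mean, BLQ missing | Median, BLQ missing | Mean, BLQ = 0 |
|---|---|---|---|---|
| 1/3 | 30% | +15% | +13% | −23% |
| 1/3 | 50% | +23% | +23% | −18% |
| 1/3 | 80% | +31% | +35% | −13% |
| 1/2 | 30% | +23% | +22% | −38% |
| 1/2 | 50% | +36% | +38% | −32% |
| 1/2 | 80% | +52% | +61% | −24% |

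**How often it would bite in a group of 6**

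- At least one BLQ trough: 1 − (2/3)⁶ = 91% at p = 1/3, and 1 − (1/2)⁶ = 98% at p = 1/2.
- Fewer than 3 quantifiable, so no mean is shown: 73/729 = 10% at p = 1/3, and 22/64 = 34% at p = 1/2.

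**Six-subject illustration**

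Let the LLOQ be 1 and the true troughs 0.3, 0.5, 0.8, 1.2, 1.8 and 2.6, with mean 1.20 and median 1.0. With BLQ set to missing, n = 3, mean 1.87, median 1.8. With BLQ set to 0, n = 6, mean 0.93, median 0.6. Exactly half are BLQ here, so even the ranked median is not pinned down.

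**The case against.** Several points on the other side have weight.

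- **Which profile the sample belongs to.** The sample before the next dose may be read as closing one profile or opening the next. In the second reading it need not be trailing, and the default of 0 could apply. This stands as a condition on the point. It also shows that the SAP does not settle what happens to a BLQ trough.
- **Whether the sample exists.** For the last dose, 72 h falls on Day 16, after residence ends on Day 15 and before the nominal Day 18 (±2 days) visit. This limits the point for the final interval. The first four intervals end on dosing days during residence.
- **Visibility.** All concentrations are listed and n is reported, so a Ctrough n of 4 out of 6 would be seen. That reveals the loss but does not correct the mean or median beside it.
- **Importance.** PK is exploratory, Ctrough is not named among the Section 3 endpoints, and an upward bias is cautious for the exposure-limit endpoint. This limits the priority.
- **Two BLQ conventions are normal.** Parameter derivation and concentration tables often differ, and the SAP says so openly. That is fair for AUC. It is weaker for Ctrough, which is simply a concentration.
- **Setting BLQ to 0 is no cure for the mean.** This stands. At a CV of 30% the downward bias (−23% and −38%) exceeds the upward bias of the rule as written (+15% and +23%).

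A reader might also infer that AUC0-τ, the accumulation ratios and Cmin are reported only for subjects with high troughs. The SAP does not support that. Nothing in it drops AUC0-τ when the last quantifiable time precedes the end of the interval. Section 8.5.1.3 asks for 3 consecutive quantifiable values with at least one after Cmax, and the SAP leaves open how the rest of the interval is handled. For Cmin, removing a BLQ value does not remove the subject: the minimum falls back to another value, or to 0 if a BLQ predose value counts.

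**Conclusion.** The point holds for Ctrough. Applied as written, and where the end-of-interval sample belongs to the preceding profile, Section 8.5.1.1 turns a BLQ trough into a missing one and restricts the Part B Ctrough summary to quantifiable values, while Section 8.5.2 counts the same sample as 0.

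The sizes in the table show what the rule can do and do not predict this trial. They rest on lognormal troughs and on assumed CVs and BLQ shares. If no troughs are BLQ, there is no effect. BLQ values are nevertheless foreseeable, since the SAP provides for wholly BLQ profiles and plans PK only where it can be determined.

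The point does not extend to AUC0-τ or to accumulation. For Cmin it goes no further than the need to say how BLQ values enter if that parameter is derived. The change is worth making before database lock, but no safety conclusion is shown to depend on it.

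**What to change.** In Section 8.5.1.1, limit the rule that sets trailing BLQ values to missing to AUC calculation and terminal-slope estimation. Then add wording to this effect:

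- For Ctrough, and for Cmin if it is derived, a BLQ end-of-interval value is reported as BLQ and ranked below all quantifiable values.
- The main summary is the number BLQ, median, minimum and maximum. The ranked median is fixed by the data while fewer than half of the group are BLQ. Otherwise it is marked as not estimable, and the number BLQ and the maximum carry the information.
- If a mean with BLQ as 0 is also shown, it is labelled as biased low (about 13% to 23% at one third BLQ under the assumptions above).
- A predose sample that ends one dosing interval and begins the next counts as the trough of the earlier interval.

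Section 8.5.1 should also say whether Cmin is derived, since Section 3.2 lists it and the parameter table does not.

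The cost is SAP wording and one extra row in the Part B parameter table. The downside is that the mean becomes a less informative, secondary figure.

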## 8.5.1.2. Criteria for the Calculation of an Apparent Terminal Elimination Half-Life

### 8.5.1.2.1. Number of Data Points

• At least 3 data points will be included in the regression analysis and preferably should not include  $C_{\text{max}}$ .

## **8.5.1.2.2.** Goodness of Fit

- When assessing terminal elimination phases, the adjusted coefficient for determination of exponential fit (R^2-adj) will be used as a measure of the goodness of fit of the data points to the determined line.
- Regression based parameters (AUC0- $\infty$ , t1/2) will only be calculated if the R^2-adj  $\geq$ 0.7.

## 8.5.1.2.3. Period of Estimation

- Time period used for the estimation of  $t_{1/2}$ , where possible, will be over at least 2 half-lives. The regression listing will include the time period over which the  $t_{1/2}$  was derived as a ratio of the determined  $t_{1/2}$  for each subject.
- Where an elimination half-life is estimated over a time period <2 half-lives, it will be flagged in the data listings at the discretion of the pharmacokineticist, and the robustness of the value should be discussed in the CSR.

#### 8.5.1.3. Calculation of AUC

- The minimum requirement for the calculation of AUC will be the inclusion of at least 3 consecutive plasma concentrations above the lower limit of quantification (LLOQ), with at least 1 of these concentrations following Cmax.
- For any partial AUC determination (i.e. AUC over a dosing interval), nominal time will generally be used for the end of the interval. Actual times for partial AUC intervals may be used at the discretion of the Pharmacokineticist.

• AUC0-∞ values where the percentage extrapolation <20% will be reported. AUC0-∞ values where the percentage extrapolation is between 20 to 30% will be flagged and included in the summary statistics, whilst AUC0-∞ values where the percentage extrapolation is >30% will be reported and flagged but excluded from summary statistics.

• If AUC0-∞ cannot be determined for all subjects or all dose levels, an alternative AUC measure, such as AUC to a fixed time point, may be used in the assessment of dose proportionality.

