## Primary PK

- o AUC over a dosing interval (AUC0- $\tau$ ) (actual and DN)
- o AUC0-∞ (actual and DN)

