#### **4.2. Part B**

Part B will comprise a multiple-dose, sequential-group study. Overall, 32 subjects will be studied in 4 groups (Groups B1 to B4), with each group consisting of 8 subjects. Up to 2 additional groups (16 subjects in total) may be included for further assessment of safety and tolerability.

Potential subjects will be screened to assess their eligibility to enter the study within 28 days prior to the first dose administration. Each subject will participate in 1 treatment period only and reside at the CRU from Day -1 until Day 15.

All subjects will return for non-residential visits on Days 18 ( $\pm 2$  days), 22 ( $\pm 2$  days), 25 ( $\pm 2$  days), and 29 ( $\pm 2$  days), and for a poststudy visit on Day 57 ( $\pm 2$  days).

In each of Groups B1 to B4, 6 subjects will receive OLP-1002 and 2 subjects will receive placebo. For all subjects, a single SC dose will be administered on Days 1, 4, 7, 10, and 13. Prior to each dosing occasion a physician will review the available safety and tolerability data from each subject to confirm it is acceptable to continue dosing. The dosing frequency in Part B may be changed following review of data from groups in Part A.

Sentinel dosing will only occur in Part B at dose levels where exposure to OLP-1002 at steady state is predicted to exceed exposures that have been shown to be safe and well

Covance Study: 8379789

[figure not shown]
tolerated in earlier groups in Parts A or B. In the event of sentinel dosing, 2 subjects (1 active, 1 placebo) will be dosed at least 4 days prior to the remaining 6 subjects (5 active: 1 placebo). Safety data for the sentinel subjects from at least 2 additional doses will be reviewed prior to dosing the remaining subjects (i.e. sentinel subjects' safety data after doses 1 and 2 will be reviewed prior to the remaining subjects receiving dose 1). In addition, safety data from each subject will be reviewed by a physician prior to each dose to approve continued dosing.

Doses will be administered in an escalating manner following satisfactory review of safety, tolerability, and PK data up to Day 22 (216 hours post-final dose) from the lower dose levels. Part B may start after a review of the safety, tolerability, and available PK for Groups A1 to A6. The total daily dose administered will not exceed the highest single dose given in Part A.

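### In Part B the >30% extrapolation exclusion, applied to a Day 1 profile cut off at 72 h, selects subjects by elimination rate, and its flag is not carried to TCP

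*SAP*

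**What the plan says.** - **Schedule.** In Part B (SAP 4.2) "a single SC dose will be administered on Days 1, 4, 7, 10, and 13". Within each of Groups B1 to B4, "6 subjects will receive OLP-1002 and 2 subjects will receive placebo".
- **Status of AUC0-∞.** The Part B list under Primary PK (SAP 3.2) includes "AUC 0-∞ (actual and DN"). That list sits within the exploratory endpoints.
- **TCP.** SAP 8.5.1 lists "temporal change parameter, calculated as" the ratio of AUC0-τ on profile day 15 to AUC0-∞ on profile day 1. No extrapolation limit is attached.
- **Exclusion rule.** Under SAP 8.5.1.3, AUC0-∞ with less than 20% extrapolation is reported. Values at 20 to 30% are flagged and summarised. A value whose extrapolation "is >30% will be reported and flagged but excluded from summary statistics". The rule names AUC0-∞ only and applies to both parts.
- **Extrapolated share.** SAP 8.5.1 defines it as the "percentage of AUC that is due to extrapolation from the last measurable plasma" concentration onward. Under SAP 8.5.1.1, "BLQ values following the last quantifiable concentration in a profile will be set to missing", so the last usable point can fall before 72 h.
- **Small numbers.** SAP 8.1.1: "If number of subjects with valid observations (n) <3, summary statistics will not be calculated", apart from n, minimum and maximum.
- **Whether AUC0-∞ is summarised.** SAP 8.5.1.2.2 counts AUC0-∞ among the regression-based parameters. SAP 8.5.3 leaves regression-related parameters out of the summary tables. The rule in 8.5.1.3 presupposes that AUC0-∞ is summarised.

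**The concern.** A limit on extrapolation is a quality check when the sampling window is long compared with the half-life. In Part B the Day 1 window is fixed by the second dose. A large extrapolated share can then simply mean that the subject eliminates slowly and will accumulate. The filter is therefore related to the quantity being summarised, and to the accumulation that Part B also sets out to measure.

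Three things are at stake:

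- The Part B Day 1 AUC0-∞ and dose-normalised AUC0-∞ summaries may describe a selected subset of each group of 6 active subjects.
- TCP, the check for time-dependent kinetics, may rest on a different set of subjects, including denominators that were left out of their own summary. The two results would then be hard to read together.
- SAP 3.1 makes exposure relative to nonclinical limits a primary safety endpoint but names no exposure metric. A selected exposure summary supports it poorly.

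**Working it through.** The SAP states no figure for bias or precision of AUC0-∞, so there is none to reproduce.

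**1. Length of the Day 1 profile.** The gap from Day 1 to Day 4 is 3 days = 72 h. First-dose data cannot run beyond 72 h.

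**2. Where the 30% cut falls.** Take mono-exponential decline with rate k, quantifiable to 72 h:

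- Extrapolated fraction f = exp(−72k), with k = ln 2 / half-life.
- Accumulation ratio R = 1/(1 − exp(−72k)) = 1/(1 − f).
- Setting f = 0.30 gives half-life = 72 × 0.693 / ln(1/0.30) = 49.9 / 1.204 = 41.5 h, and R = 1/0.70 = 1.43.
- Half-lives of 12, 24, 36, 48 and 72 h give f = 1.6%, 12.5%, 25%, 35% and 50%.
- For comparison, a profile of 216 h, the PK review window after the final dose, moves the 30% cut to 3 × 41.5 ≈ 124 h.

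**3. Effect on the retained summary.** The SAP gives no half-life, variability, assay limit or sampling times, so these are assumptions: one-compartment SC model, absorption rate 1/h, 12 samples over 72 h, 10% residual error, linear-up/log-down AUC, adjusted R² at least 0.7, then the 30% rule, with 3,000 subjects per scenario. The geometric mean ratio is that of the retained values to the truth in all subjects.

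| Source of variation | Median half-life (h) | Share kept | Geometric mean ratio | Chance of fewer than 3 of 6 |
|---|---|---|---|---|
| Clearance, log-SD 0.4 | 24 | 90% | 0.93 | not tabulated |
| | 36 | 62% | 0.78 | 0.15 |
| | 41.4 | 51% | 0.74 | 0.32 |
| | 48 | 36% | 0.66 | 0.62 |
| Clearance and volume, 0.3 each | 24 | 88% | 0.95 | 0.00 |
| | 41.4 | 50% | 0.84 | 0.34 |
| | 60 | 21% | 0.74 | 0.89 |
| Volume, log-SD 0.4 | 24 | 90% | 1.00 | 0.00 |
| | 41.4 | 50% | 0.98 | 0.35 |
| | 60 | 20% | 0.96 | 0.91 |

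In the clearance-only case, half-lives of 6 to 12 h lose no one and the ratio is 0.99 to 1.00.

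**4. Profiles shortened by the assay limit.** Assume bioavailability varies with log-SD 0.4, clearance and volume with 0.2 each, and the limit lies at 10 to 40% of the typical initial concentration. The ratio is 1.06 to 1.82 at 12 h, 1.03 to 1.66 at 24 h and 0.91 to 1.48 at 41.4 h. At 12 and 24 h it is mainly low-exposure subjects who are lost, so the bias is upward.

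**5. Limits of the 1.43 equivalence.** The rule uses the estimated extrapolated share, from a slope fitted within 72 h. Consider noise-free biexponential decline with half-lives of 12 h and 150 h and a 10% slow component:

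- Total area is proportional to 0.9×12 + 0.1×150 = 25.8.
- Area beyond 72 h is proportional to 10.8×2^(−6) + 15×2^(−0.48) = 0.17 + 10.75 = 10.92.
- The true share is 10.92/25.8 = 42%, so R = 1.73. The share estimated from the 72 h slope is about 15%, and the subject is kept.

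With 20 h, 100 h and a 20% slow component, the true share is 13.46/36 = 37% and R = 1.60. The estimate is about 22%, and the subject is again kept.

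**6. TCP.** Its denominator is the Day 1 AUC0-∞. Sections 8.5.1 and 8.5.1.3 neither exclude nor flag a TCP whose denominator exceeded 30% extrapolation.

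**The case against.** A reader might infer that the rule biases Part B AUC0-∞ low and drops every subject with an accumulation ratio above 1.43, whatever the kinetics. The documents do not support that. The SAP gives no half-life. The effect vanishes for short half-lives, is slight when volume drives variation, and can reverse when the assay limit truncates profiles, which SAP 8.5.1.1 anticipates. The biexponential examples in the working show high accumulators being kept. This part of the objection stands in full.

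Other points limit the importance:

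- Read literally, 8.5.1.2.2 and 8.5.3 together mean AUC0-∞, and arguably TCP, would be listed but not summarised. That is possible, but 8.5.1.3 then has no purpose, so the text still needs correcting.
- PK is exploratory and no inferential analysis is planned. Excluded values stay in the listings, and AUC0-τ, Cmax and the two accumulation ratios are untouched by the rule. This lowers the stakes but does not remove the defect.
- SAP 4.2 allows the dosing frequency to change, so 72 h is the planned interval only. The cut moves with the interval; the mechanism remains.
- That TCP keeps the flagged values is read from silence. As written, however, nothing removes or marks them.
- Summarising every value trades selection for extrapolation error, which the rule exists to limit. That argues against dropping the rule, not against showing both summaries.

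The optional alternative AUC in 8.5.1.3 does not close the gap, because it is tied to dose proportionality.

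**Conclusion.** The concern holds in conditional form. With doses 72 h apart, the 30% rule makes inclusion in the Part B Day 1 AUC0-∞ summaries depend on elimination and accumulation. The equivalence to a half-life above 41.5 h or an accumulation ratio above 1.43 requires mono-exponential decline quantifiable to 72 h.

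Bias is downward when clearance drives variability and half-lives approach or exceed about 30 to 40 h (ratio 0.78 at 36 h, 0.66 at 48 h). It is near zero for short half-lives or volume-driven variation, and possibly upward when the assay limit shortens profiles. All these ratios rest on the assumptions listed in the working, so neither size nor direction can be fixed from the SAP.

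Separately, AUC0-∞ and TCP may rest on different subjects because the flag stops at AUC0-∞. This should be corrected; it does not threaten the trial's primary safety assessment.

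**What to change.** Keep the >30% flag, and do not waive the exclusion outright for Part B. In SAP 8.5.1.3 and 8.5.3:

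1. State which Part B profile supplies AUC0-∞.
2. For Day 1, report per dose the number with more than 30% extrapolation. Show AUC0-∞ and dose-normalised AUC0-∞ with and without the flagged values, beside AUC0-τ.
3. Carry the same flag to TCP and present TCP with and without flagged subjects.
4. Reconcile 8.5.1.2.2 and 8.5.3 with 8.5.1.3 on whether AUC0-∞, and with it TCP, is summarised.
5. Do not extrapolate the TCP denominator with the slope after the final dose. That assumes the time-invariance TCP is meant to test.

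While editing TCP, also reconcile its profile day 15 with SAP 4.2, where the last planned dose is on Day 13.

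The cost is SAP wording and one extra column or table, with no new samples or subjects. The drawback is that the all-subject column carries more extrapolation error. In the clearance-only simulations, all values with an acceptable fit gave a geometric mean of 0.98 of the truth at 48 h and 0.92 at 72 h, but those runs assume mono-exponential decline and so flatter the extrapolation. With the assay limit at 40% of the initial concentration and a 12 h half-life, the figure was 1.31. Neither column is safe alone, so both should be shown.
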